Hypertension is a major cause of both mortality and morbidity in the UK. Oversecretion of the hormone aldosterone is implicated in around 30% of cases of hypertension seen in secondary health care. At present very few of these patients with hyperaldosteronism are diagnosed as the protocols for diagnosis are complex and invasive. In a recent study, we developed a technique for the continuous monitoring of aldosterone using a novel device called U-Rhythm[1] and found that this was able to differentiate abnormal aldosterone secretion in many cases. In order to improve our diagnostic efficacy we need to show whether changing the dietary input of salt can inhibit aldosterone secretion in normal subjects but not in people with hyperaldosteronism. We first need to do a pilot study to see how changes in salt intake alter the 24-hour regulation of aldosterone in normal subjects.

The aim of our study is to assess whether high or low salt diet affects aldosterone levels for a healthy individual over a 24-hour period.

Our proposed project would involve recruiting 12 healthy volunteers and asking them to adhere to a high or low salt diet for 7 days before using the U-Rhythm technique to monitor aldosterone (and additional hormones) for 24 hours. We will also collect a 24-hour urine sample to measure sodium and aldosterone levels, and blood tests for renin and aldosterone (lying and standing) and renal function (including electrolytes). Additionally, we will ask the participants to exercise on a static bike as aldosterone has been shown to change after exertion[2,3]. After a washout period the process will be repeated following 7 days adhering to the alternate diet. All dietary regimens have been prepared by NHS dietitians and will be balanced in all other nutritional components.

2. Sponsor details

University of Bristol

[name], Head of Research Governance, University of Bristol.

Division of Research, Enterprise and Innovation, [name]. [contact]. Email: [contact]

Sodium intake effect on Aldosterone Level in real Time (SALT) Study protocol v3 31/07/2025

IRAS: 354064

3. Chief investigator and research team

Chief Investigator

[name], Ph.D. Senior Lecturer in Cardiovascular Physiology, School of Physiology, Pharmacology & Neuroscience, [name]. Tel (mob): [name], [contact]. Email: [contact]

Co-Investigators

Salt intake is known to effect plasma renin activity and consequently aldosterone concentration. This was not controlled in the U-Rhythm pilot study. We hypothesise that variation in salt intake may, at least in part, explain the different patterns observed. If the hypothesis is correct, we would expect a high salt diet to lead to a diurnal (ACTH dependent) pattern of aldosterone as we expect salt would reduce the levels of renin and angiotensin 2. Conversely, we would expect a low salt diet to result in greater levels of renin and angiotensin 2 resulting in a non- ACTH dependent ultradian rhythm of aldosterone concentration.

[figure not shown]

Figure 1: Figure from Upton et al (2003)[1] showing how cortisol and aldosterone varied in 2 healthy volunteers. Note how aldosterone (blue line) follows cortisol (red line) closely in panel B, however there is very little correlation in panel C. We wish to explore whether salt intake may explain the difference in healthy volunteers.

Learning how salt intake affects dynamic changes in aldosterone secretion- especially overnight- may lead to improved methods for diagnosing abnormal patterns of aldosterone levels and thereby allow improved therapy.

5. Aims and hypothesis

5.1 Primary aim

To assess whether altering salt intake for a healthy individual affects their aldosterone profile over a 24-hour period.

5.2 Hypothesis

The high salt diet and low salt diet will have difference aldosterone profiles. Specifically, we expect the high salt diet will lead to a diurnal rhythm (as renin may be suppressed, meaning the dominant regulatory factor is ACTH) and low salt diet an ultradian rhythm (with renin as the primary regulator).

5.3 Null hypothesis

There will be no difference in aldosterone profiles between study arms.

6. Participants and recruitment

6.1 Sample size and power calculation

For this pilot study we will recruit 12 healthy volunteers.

6.2 Inclusion criteria

All participants:

Aged 18-40 years

6.3 Exclusion criteria:

All participants:

- A history of hypertension, hyperaldosteronism, obstructive sleep apnoea, or heart disease.
- Taking medication that could affect aldosterone levels. This includes most antihypertensives and common inhalers.
- Anyone with a 1st degree family member who was diagnosed with hypertension below the age of 60 or has a diagnosis of primary hyperaldosteronism.
- Inability to understand spoken or written instructions given in English
- Body mass index ≥30 kg/m²
- Pregnancy

Sodium intake effect on Aldosterone Level in real Time (SALT) Study protocol v3 31/07/2025

IRAS: 354064

- Alcohol consumption (>28 units/week), daily use of nicotine (including smoking and vaping) and daily use of recreational drugs due to risk of withdrawal symptoms during lab visits
- Needle phobia
- Allergy to any ingredient within meal plans, or dietary requirements that cannot be catered for within the meal plans
- Anyone who has worked shifts finishing after midnight in the past 4 weeks
- Anyone with irregular sleep times (i.e. bedtime/wake time varies by more than +-1 hour across a normal week)

6.4 Recruitment

Participants will be recruited via posters and leaflets displayed around the University of Bristol and public spaces in the wider area (e.g. local shops, cafes, community centres and GP reception areas); study adverts placed in community/University newsletters; study adverts emailed through University Faculty email; information on our research groups website, http://www.uhbristol.nhs.uk/hypertension; and finally social media posts.

Permission will be gained before posters/leaflets are left in public spaces and before adverts are emailed through university email.

Additionally, individuals that have given permission for the research group to store their contact details and to be contacted about taking part in studies may be invited to take part in the study.

7. Study design

This will be an open-label crossover study. We shall recruit 12 volunteers aged 18-40. All subjects will be screened with a general health history, recording of blood pressure, electrocardiogram and blood tests (renal function, electrolytes, and thyroid stimulating hormone).

The subjects will undergo 2 different manipulations of their sodium intake using dietary regimens have been prepared by NHS dietitians and will be balanced in all other nutritional components. The sodium intake in each protocol is listed below:

- 1) 7 days low salt diet (<400 mg sodium per day)
- 2) 7 days high salt diet (around 5.9g sodium per day)

Participants will be asked to adhere to both protocols, with at least a week's washout in between. On the final day of each protocol the subject will have 24-hour interstitial

Study protocol v3 31/07/2025

IRAS: 354064

steroid sampling using our U-rhythm system[1] and 24-hour urinary sodium and

aldosterone measurement.

Day of study	Events	Location
Pre- study	Screening questionnaire issued via phonecall and study visits booked if eligible.	Telephone
Day 0	 Study visit 1 (1 hour) [labelled visit 4 on 2nd arm of study] Meet at NIHR Clinical Research Facility Consent form BP check, ECG, urinalysis, blood tests (U&E, TSH) Give meals for the week or arranges time for delivery VO2 peak test on static bike (to provide reference for exercise test at visits 3 and 6) Gives 24-hour urine collection bottle Calibrates and loans Aktiia optical blood pressure monitor Loans motion-watch or similar 	NIHR Clinical Research Facility (CRF), [name]
Day 1-6	Participant follows meal plan and keeps sleep diary Contact researcher if any issues (study email address: [contact] or designated phone number)	
Day 7	Participant starts 24-hour urine collection with 2 nd micturition of the day Study visit 2 (1 hour) [labelled visit 5 on 2 nd arm of study] - U-Rhythm set-up - Given sleep-recording device (Acu-Pebble or similar) - Given 24-hour diary Participant completes 24-hour diary (recording meal times,	NIHR CRF, [name]
Day 8	sleep/wake times and any exercise undertaken). 24-hour urine finishes after 1 st micturition of the day Study visit 3 (4 hours) [labelled visit 6 on 2 nd arm of study] - Weight and blood pressure measured - Participant adopts supine posture on arrival - Post-diet questionnaire - Blood tests (U&E, renin, and aldosterone after 30 mins lying then at 20, 40, and 60 minutes standing plus stored samples for future analysis) - Exercise on static bike (30 minutes at 50-60% VO2 peak) - Serum renin and aldo after exercise - U-rhythm disconnected 2 hours after exercise finish	NIHR CRF, [name]

- 24-hour urine sample, U-rhythm, and sleep device returned
- Diet protocol stopped after visit (i.e. after breakfast on day 8)
 unless there has been any issue with U-rhythm recording, in
 which was the participant will be asked to extend the study for a
 further day and conduct a full visit 3 or 6 the next day

If this is the participant's first arm of the study, arrange dates for 2^{nd} arm.

£150 compensation for time given in voucher form after completion of each arm of the study.

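### The protocol sets no randomised or counterbalanced diet order, so a period effect cannot be excluded as an explanation of a high-versus-low salt difference

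*Protocol*

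**What the plan says.** Section 7 (Study design) gives the design in a few words: "This will be an open-label crossover study. We shall recruit 12 volunteers aged 18-40". It lists two diets, low salt as item 1 and high salt as item 2, each lasting 7 days, and adds: "Participants will be asked to adhere to both protocols, with at least a week's washout in between".

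The opening summary describes the first period as "asking them to adhere to a high or low salt diet for 7 days before using the U-Rhythm technique", and the second as follows: "After a washout period the process will be repeated following 7 days adhering to the alternate diet".

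The visit table in section 7 relabels visits 1 to 3 as visits 4 to 6 for the second arm. On Day 8 it adds only an instruction on scheduling, which begins "If this is the participant's first arm of the study, arrange dates for 2". It does not say which diet is supplied on Day 0 of the first arm.

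Section 6.1 says "For this pilot study we will recruit 12 healthy volunteers", with no derivation. Randomness is mentioned in only two places: section 14.1, for the sample of case report forms to be checked, and section 13.2, as one way to order authors. The text contains no sequence allocation, counterbalancing or other rule for diet order.

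**The concern.** In a two-period crossover each person is their own control, but the two measurements are taken at different times. Anything that shifts the second period relative to the first shifts the within-person difference too. The direction of that shift depends on which diet came first, so it cancels only if the orders are balanced.

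Period effects are plausible here. By the second period the volunteer has already had the catheter, the overnight recording and the exercise session. The washout has a minimum of one week and no maximum, and second-arm dates are arranged individually after the first arm. Part of the hypothesis in section 5.2 concerns a diurnal, ACTH-driven rhythm, which a first experience of an indwelling catheter might affect. The protocol gives no data on this.

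Because the study is open-label and no rule is given, order could be settled by convenience, by the volunteer's preference, or by staff who know the diets. The primary outcome and every secondary outcome in section 8 are differences between diets, so all are exposed.

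**Working it through.** **Inputs from the protocol.** Twelve participants, two diets, two periods, each person taking both diets (sections 6.1 and 7). The split between orders is not given.

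**Inputs assumed.** The protocol states no significance level, standard deviation, effect size or period effect, so it has no figure of its own to reproduce. I assume a two-sided 5% paired t-test and express the period effect in units of the SD of the within-person difference (the SD within one order), over a range of 0.25 to 0.75.

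**Step 1: bias.** Let D be high minus low, τ the true diet effect and π the period effect (second minus first).

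- Low first: E[D] = τ + π.
- High first: E[D] = τ − π.
- Mean over all 12: τ + π × (n_LH − n_HL)/12, where n_LH is the number taking low first and n_HL the number taking high first.

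For example, at 9:3 the factor is (9 − 3)/12 = 0.50, and at 8:4 it is (8 − 4)/12 = 0.33.

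**Step 2: false-positive rate when all 12 share one order.** With no true diet effect, the t statistic on 11 degrees of freedom is noncentral, with noncentrality π√12 (π in SD units). The critical value is 2.201.

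- 0.25 SD: 0.25 × 3.464 = 0.866, rejection 12.4%.
- 0.5 SD: 1.732, rejection 35.3%.
- 0.75 SD: 2.598, rejection 65.8%.

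**Step 3: mixed orders, same unadjusted test, by simulation.**

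| Split (low-first : high-first) | Bias as share of π | False positives at 0.25 / 0.5 / 0.75 SD | Variance of period-adjusted estimate relative to 6:6 |
|---|---|---|---|
| 6:6 | 0 | 4% / 3% / 2% | 1.00 |
| 8:4 | 33% | 5% / 6% / 6% | 1.125 |
| 9:3 | 50% | 6% / 9% / 12% | 1.33 |
| 12:0 | 100% | 12% / 35% / 66% | not estimable |

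The last column is 3 × (1/n_LH + 1/n_HL); at 8:4, 3 × (1/4 + 1/8) = 1.125. The false-positive rate barely moves at 8:4 because an unmodelled period effect also widens the spread of the differences. The bias in the estimate remains.

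**Step 4: cost of fitting period at 6:6.** Error degrees of freedom fall from 11 to 10, and the critical value rises from 2.201 to 2.228. The ratio is 1.012, so the confidence interval is about 1.2% wider at the same residual SD.

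**Step 5: why a blocked list.** With a coin-flip for each of 12 people, a split of 8:4 or worse has probability 0.39, and 9:3 or worse 0.15.

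**The case against.** A reader might infer from the numbering in section 7 that all 12 take low salt and then high salt, so that diet and period are completely confounded. The text does not support that. The numbers introduce a list of sodium intakes and fix no sequence. The summary's wording, a high or low diet first and then the alternate one, reads more naturally as both orders occurring. The 12%, 35% and 66% rates therefore belong to one conditional scenario. At 8:4 there is almost no inflation of the false-positive rate. With any mix of orders a period term can be fitted, and whether it will be may be settled in an analysis plan that is not shown.

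It can also be said that this is a pilot with no stated significance threshold, that nothing in the protocol anchors the size of a period effect, and that the diets differ about 15-fold in sodium (5.9 g against 400 mg: 5,900/400 = 14.75).

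These points limit the size of the problem but do not remove it. Order is fixed when meals are supplied for the first arm, so an analysis plan cannot create balance afterwards. A period term corrects for period, but if order was chosen and not randomised, the two sequence groups may differ in other ways. Pilot or not, the protocol states a hypothesis and a null and intends the result to inform a diagnostic approach.

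**Conclusion.** The concern holds as a gap in the design: diet order is left unspecified, so the plan does not protect the high-versus-low comparison from a period effect. The size depends on a split that the protocol does not fix. Bias in the unadjusted difference runs from none at 6:6, through one third of the period effect at 8:4 and one half at 9:3, to all of it at 12:0. Only at 12:0 is separation impossible by any analysis.

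The bias fractions follow from the design alone. The false-positive rates also rest on the assumed 5% paired t-test and the assumed range of period effects. The finding does not claim that a period effect exists, nor that a single order will be used. It should be settled before the first volunteer receives meals, because order cannot be repaired later.

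**What to change.** State in section 7 that this is a randomised two-period, two-sequence crossover, with 6 participants taking low then high and 6 taking high then low. Use a computer-generated blocked list and reveal each participant's sequence only after eligibility is confirmed. Since the visit table has meals supplied or their delivery arranged at visit 1, set out there when the sequence is revealed relative to the screening checks. Include period as a factor in the within-person analysis, here or in the statistical analysis plan.

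The cost is a short amendment, a 12-line allocation list and one degree of freedom. The sample size, visits and tests do not change.

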9.1.5 Pregnancy testing

Premenopausal females will be asked to confirm that they are not pregnant and will be offered a pregnancy test prior to participating in the study to confirm they are not pregnant. This test is mandatory. The urine pregnancy test will be completed on all visit days (before commencing any procedures) by a researcher or research nurse.

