9.7 Sex/Minority Mix

Males and females of all ethnic groups will be eligible to participate in the study. We will aim to recruit members from the BAME community. Bristol has a large BAME community, and this is represented in our healthcare workforce. We will engage with local representatives of the BAME community through the staff BAME committee in the hospital to identify any concerns and find ways to maximise participation.

10. Reporting incidental findings

It is possible that incidental findings concerning participants' health could be identified during the study, for example abnormality in the ECG, blood pressure or pregnancy test. Should incidental findings be identified, both the participant and their GP will be informed. Permission will be gained before a participant's GP is informed of incidental findings. If the participant does not want their GP informed, only the participant will be informed of any findings; however, a letter will be written to the participant to inform them of the findings.

11. Data handling, confidentiality and disposal

Personalised study data will be maintained at the University of Bristol in paper and/or electronic format. Both paper and electronic records will be kept in a locked cupboard in a locked room in a department with security-limited access. Access to the records is restricted to researchers working on the study. Password protection will be used for electronic data and, for the purposes of data analysis, anonymised data will be held on an encrypted flash drive, to be locked as above when not in use. No identifiable data will be stored on laptop computers or portable electronic devices. Analysis will take place by the study team led by [name] and collaborators (using anonymised data). Data will be collected and retained in accordance with the Data Protection Act 2018. Study documents (paper and electronic) will be retained in a secure location during and after the trial has finished. All source documents will be retained for a period of fifteen years following the end of the study. Where trial related information is documented in the medical records – those records will be identified by a 'Do not destroy before dd/mm/yyyy' label where date is fifteen years after the last patient last visit.

Sodium intake effect on Aldosterone Level in real Time (SALT) Study protocol v3 31/07/2025

IRAS: 354064

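### The protocol sets only a minimum washout and neither aligns nor records menstrual phase, so phase may be mixed with diet in cycling women, mainly as added variance

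*Protocol*

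**What the plan says.** Section 7 (Study design) describes an open-label crossover of two 7-day diets, one below 400 mg and one around 5.9 g of sodium per day. On spacing it says "Participants will be asked to adhere to both protocols, with at least a week" of washout between them. On timing of the measurement it says "On the final day of each protocol the subject will have 24-hour interstitial" steroid sampling. The visit table in the same section sets up the sampling on Day 7 and ends the diet at the Day 8 visit. For the interval between arms the table says only, for the participant's "first arm of the study, arrange dates for 2^{nd} arm".

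Section 6.2 sets the age range at 18 to 40. Section 9.7 states "Males and females of all ethnic groups will be eligible to participate in the study". Section 9.1.5 expects premenopausal women: "Premenopausal females will be asked to confirm that they are not pregnant", with a urine test on every visit day. Pregnancy exclusion and testing are the only reproductive provisions. The 24-hour diary covers meals, sleep and exercise, not cycle day. The medication exclusion in section 6.3 does not mention hormonal contraception.

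Section 8 makes the primary outcome the difference in aldosterone profiles, by cosinor analysis and by dynamic markers: area under the curve, morning peak, number of peaks or evening nadir.

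**The concern.** A crossover removes stable differences between people. It does not remove an influence that changes within a person between the two periods. Menstrual phase is such an influence if it affects aldosterone, and the shortest interval the protocol allows is close to the least favourable one for a cycle of about 28 days.

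The protocol already guards against other within-person disturbances: it excludes drugs that affect aldosterone, recent late shifts and irregular sleep times. Section 4 says that salt intake was not controlled in the earlier pilot and may explain the differing patterns seen there. The present study is meant to isolate that one source of variation, so leaving another likely source uncontrolled and unrecorded works against its purpose. With 12 participants there is little precision to spare, and a cycle day that was never collected cannot be adjusted for later.

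**Working it through.** The protocol states no interval between recordings and no power figure, so there is nothing of its own to reproduce.

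**Interval between recordings.** Inputs from section 7: recording starts on Day 7, diet stops on Day 8, washout W is at least 7 days.
- Washout counted from Day 8: the second arm's Day 1 is Day 8 + W and its recording starts on Day 14 + W. The gap is 14 + W − 7 = W + 7.
- Only full days from Day 9 counted: the gap is W + 8.

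| Washout (days) | Gap (days) |
|---|---|
| 7 (minimum) | 14–15 |
| 14 | 21–22 |
| 21 | 28–29 |

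**Share of cycling women recorded in different phases.** Assumptions, not in the documents: cycle length L, luteal phase 14 days, first recording on a random cycle day. With g the gap (modulo L), the share is 2 × min(g, L − g, 14, L − 14) / L.
- L = 28, g = 14: 2 × 14/28 = 100%. L = 28, g = 15: 2 × 13/28 = 93%.
- L = 24: g = 14 gives 2 × 10/24 = 83%; g = 15 gives 2 × 9/24 = 75%.
- L = 35: g = 14 or 15 gives 2 × 14/35 = 80%.
- Averaged over L = 24 to 35: about 90% for g = 14 and 86% for g = 15.
- 14-day washout, L = 28: g = 21 gives 2 × 7/28 = 50%; g = 22 gives 2 × 6/28 = 43%.
- 21-day washout, L = 28: 0 to 7%. The same gap of 28 days gives 33% for L = 24 and 40% for L = 35, so matching on cycle day is better than a fixed 28 days.

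**Effect on precision.** Let s be the SD of the log diet difference without any phase effect, r the ratio of aldosterone between phases, and p the share of participants recorded in different phases. If either phase is equally likely to meet either diet, each such woman's difference shifts by +ln r or −ln r. The variance becomes s² + p(ln r)², and the SD is multiplied by √(s² + p(ln r)²)/s. Assumed: s = 0.3 to 0.5, p = 0.5 or 0.25.

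| r | (ln r)² | p = 0.5, s = 0.5 to 0.3 | p = 0.25, s = 0.5 to 0.3 |
|---|---|---|---|
| 1.0 | 0 | 1.00 | 1.00 |
| 1.2 | 0.0332 | 1.03 to 1.09 | 1.02 to 1.05 |
| 1.5 | 0.1644 | 1.15 to 1.38 | 1.08 to 1.21 |

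Example: r = 1.5, s = 0.3, p = 0.5 gives √(0.09 + 0.0822)/0.3 = 1.38.

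**Chance imbalance.** With six women recorded in different phases and unrelated start dates, the phase-by-diet pairing splits 3:3 with probability 20/64 = 31%, and 5:1 or worse with probability 14/64 = 22%. A 5:1 split shifts the mean log difference by (5 − 1)/12 × ln r: a factor of 1.06 for r = 1.2 and 1.14 for r = 1.5.

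**The case against.** Four points are fairly made on the other side.

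- **The washout is a floor.** A reader might infer that every cycling woman is measured in opposite phases under the two diets. The documents do not support that. Second-arm dates are arranged individually and a longer gap can bring the phases back together. Even at the minimum, the result depends on cycle length and does not apply to women without natural cycles. This stands.
- **The phase effect comes from outside the documents.** It does, and it is treated here as an assumption with a range that includes no effect. What the documents do establish is the interval, the eligible population and the absence of any provision for phase.
- **A dramatic loss of power is not shown.** Starting from a notional 80%, a phase ratio of 2.0 with half the participants affected would cut power to 31 to 52%. That calculation fixes the diet effect at 0.886 SD, a ratio of only exp(0.886 × 0.3) = 1.30 to exp(0.886 × 0.5) = 1.56, so the cycle would have to matter more than a roughly 15-fold sodium contrast (5.9 g against 0.4 g). Were the diet ratio itself 2.0, power would stay at 88 to 97%. The protocol is a pilot with no stated power, so no target is missed. This stands too.
- **Systematic bias is not shown.** It would need first arms to cluster at one phase, which nothing suggests. If diet order were balanced, phase tied to arm number would largely cancel. The protocol does not say how order is assigned, but with unrelated start dates the effect is mainly variance.

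The illustration also concerns aldosterone level, so it bears on area under the curve, peak and nadir. No case is made here for an effect on the number of peaks or on rhythm.

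**Conclusion.** The point holds as a limited weakness of design. At the minimum washout the recordings are 14 to 15 days apart, and in an assumed 28-day cycle 93 to 100% of naturally cycling women would be recorded in different phases (75 to 100% for cycles of 24 to 35 days). Longer washouts are allowed and may lower that share, but the protocol leaves this to convenience of booking and collects nothing that would show what happened.

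The consequence rests on the assumption that aldosterone level varies with phase. Under the illustrative inputs above, with half the participants affected, the SD of the diet difference rises by 3 to 9% for a phase ratio of 1.2 and by 15 to 38% for 1.5. It rises less with fewer affected women and not at all if phase has no effect. The documents do not show that the diet comparison is biased or that the study would fail for this reason. The case for acting is that the remedy is cheap and that an unrecorded cycle day cannot be recovered.

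**What to change.** Add a scheduling sentence to section 7. For naturally cycling participants, book the second Day 7 at about the same cycle day as the first, using the participant's usual cycle length. For a 28-day cycle that is about 28 days later, a washout of 20 to 21 days (28 − 8 or 28 − 7), which the present minimum already permits. For users of hormonal contraception, use the same pack week in both arms.

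At the least, record cycle day and contraception on the case report form in each arm, so that phase can be described and, if need be, examined in a sensitivity analysis. The question can be asked when the pregnancy test is done, which already happens at every visit.

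The cost is one sentence, two form fields and about two more weeks between arms for those participants than at the minimum washout. That lengthens their time in the study and may slightly raise the risk of withdrawal. No procedure, diet or participant is added.
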